The main analyses will follow the principle of intent-to-treat, and include all 480 food insecure caregivers in the study arm to which they were allocated. We aim to minimize missing data by employing interviewer-administered surveys and communicating to participants the protections of a certificate of confidentiality. Using these strategies, item non-response ranged from 0-3% in our CRx trial. To avoid potential bias due to missing data, analyses will be conducted using multiple imputation with the chained equations method or inverse probability weighting to account for dropout and/or item non-response. In addition, characteristics of caregivers who complete each interview will be compared to caregivers who do not.

To fully leverage the longitudinal data, generalized linear mixed-effects models (GLMM) will be fit with particular interest in the time (baseline and 7, 30, 90 and 180 days and 12 months post-discharge) by study arm interaction. Based on this model, appropriate contrasts to test the intervention effect at specific time points (e.g., 12 months) will be constructed. These contrasts will permit examination of early versus late effects of the intervention, valuable information for future iterations of this and other parent/caregiver self- and family management interventions. GLMM can be used for continuous (e.g., food security score, amount of fruits and vegetables per day), ordinal (e.g., caregiver self-efficacy, food insecurity categories), or binary (e.g., enrollment in SNAP/WIC) outcomes. If there is a serious imbalance in baseline covariates despite randomization, those covariates will be included in the model. Latent growth curve modeling is a viable alternative to GLMM and will be explored when sufficient variability in the distributions of patterns of outcomes by time points exist (e.g., with the binary outcomes there will be a limited number of potential patterns).

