Aim 2. A screening-based approach to intervention is particularly important when the per individual cost of intervening is high or when the intervention has low relevance for the unaffected group. In general, healthcare-based screening is costly and, to be effective, requires ongoing training, continuous quality improvement and integration with clinical and EMR workflows. In the case of highly prevalent and potentially stigmatizing conditions like food insecurity or other unmet basic needs, a universal approach to intervention may be optimal, especially if the intervention is easily scalable and relatively low cost. In the case of CRx-H, a universal approach will not only reach food insecure people but also people who are at high risk of becoming food insecure and food secure people who may be called upon to support food insecure people in their community. We see evidence from universal implementations of CRx that 40% (CRx pragmatic trial) to 49% (HCIA CRx study) of people who received the intervention used information to help others with community resource needs. In our hospital, we also see food secure parents and other caregivers enlightened to the problem of food insecurity in our community by virtue of exposure to the Feed1st pantries during their child's hospitalization at CCH.⁴ Yet, physician concern about patient and caregiver satisfaction is a major barrier to intervening to address food insecurity.^{24,25} The purpose of Aim 2 is to demonstrate that a universal approach to delivery of the CRx-H intervention does not diminish caregiver satisfaction with care or cause caregiver or patient harm relative to usual care.

Among **all caregivers of hospitalized children (those who do and do not screen positive for food insecurity)**, evaluate the effects of CRx-H versus usual care on caregiver satisfaction with care (primary outcome), caregiver and child health (secondary outcomes) and caregiver stigma during hospitalization (secondary outcome).

Hypothesis 2a. There will be no evidence, comparing the intervention group to controls, that CRx-H decreases caregiver satisfaction with hospital care, diminishes caregiver or child health, or promotes caregiver stigma during hospitalization.

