Although the primary outcome will be caregiver satisfaction, measured as experience with hospital discharge, we will also examine other dimensions of caregiver experience with hospital care (e.g., communication with child's providers, overall hospital satisfaction). In addition, we will assess the Patient Satisfaction with Logistical Aspects of Navigation tool, which has been validated in a largely minority and low-income cancer patient population and assesses satisfaction with logistical support for navigating barriers to care and health-related information.

Analysis and Sample Size Justification Physician concern about patient and caregiver satisfaction is a major barrier to intervening to address food insecurity. To address this barrier, we hypothesize that neither satisfaction nor caregiver or child health will be significantly diminished among caregivers randomized to CRx-H compared to those randomized to usual care. Aim 2 analyses will include all caregivers enrolled in the trial (N=640).

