We will use the analytic approach described for Aim 1, following the principles of intent-to-treat. Here, we discuss analytic issues unique to Aim 2. To facilitate ease of interpretation of the primary outcome, we will linearly rescale the composite score for the Child HCAHPS dimension of satisfaction with discharge.⁵⁹ Three possible responses for each of the five items included in this dimension will be scored as: No=1; Yes, somewhat=2; Yes, definitely=3. Scores will be transformed using the formula: $y = 100 * (x-a)/(b-a)$ where y=the transformed score, x=the original score, a=the minimum possible score and b=the maximum possible score. Transformed items will be averaged to generate the composite score (range 0-100, higher values mean greater satisfaction). Of particular interest for the non-inferiority hypothesis (H2a) will be the confidence interval for the difference (usual care - CRx-H) and whether or not the upper limit of the confidence interval exceeds the non-inferiority margin. Of note, superiority of the intervention with respect to satisfaction with care, child and caregiver health, and stigma will also be tested as this can be done without penalty. Caregiver satisfaction will be measured at 7 days post discharge and will reference the index hospitalization; no longitudinal analyses will be conducted for this outcome. Typically, analyses of HCAHPS data adjust for case-mix (age, education and general health status); this will be feasible, but given the randomized design and single-site analysis, adjustment should not necessary. To determine whether there are substantial differences in the intervention's effect on food insecure compared to food secure caregivers, the intervention by food security status interaction will be tested. As in Aim 1, we will examine for differential intervention effects on primary and secondary outcomes among racial and ethnic groups, and by sex, using effect modification analyses. Some analyses will be restricted to the food secure group (N=160) to provide a more complete assessment of the impact of the intervention on this group (e.g., changes in knowledge and attitudes about food insecurity and changes in food security over time).

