The proposed sample size of 640 is sufficient based on a non-inferiority margin of 1.6 points in patient satisfaction (primary outcome), assuming group allocation 1:1, power=0.8, $\alpha=0.05$, standard deviation=8 (10% of the mean in a prior study of Adult HCAHPS). The non-inferiority margin of 1.6 points is less than the difference in this domain identified between non-Hispanic white and non-Hispanic Black adults reporting satisfaction with discharge (79.3 vs 77.4). For the analysis of changes in food security status during follow-up among the food secure group, 80 caregivers per study arm will provide 80% power ($\alpha=0.05$) to detect a 0.45 standard deviation difference in the food security score at a given time point.

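### Aim 2 sets out to show that CRx-H does no harm, but only satisfaction has a non-inferiority margin; for caregiver health, child health and stigma the only stated criterion is a lack of evidence of harm

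*SAP*

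**What the plan says.** The opening paragraph of Aim 2 in the SAP gives its purpose: to "demonstrate that a universal approach to delivery of the CRx-H intervention does not diminish caregiver satisfaction with care or cause caregiver or patient harm", compared with usual care. Hypothesis 2a is worded as an absence of evidence: "There will be no evidence, comparing the intervention group to controls, that CRx-H decreases caregiver satisfaction with hospital care, diminishes caregiver or child health". The same sentence takes in stigma as its last item: "diminishes caregiver or child health, or promotes caregiver stigma during hospitalization". Satisfaction is the primary outcome of Aim 2; caregiver health, child health and stigma are secondary.

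The Aim 2 section headed Analysis and Sample Size Justification restates the hypothesis for satisfaction and health, without naming stigma: "we hypothesize that neither satisfaction nor caregiver or child health will be significantly diminished among caregivers randomized to CRx-H". After describing how the satisfaction composite is rescaled to 0-100, it turns to the interval for usual care minus CRx-H as the basis for judging H2a, which it calls a non-inferiority hypothesis. The question put to that interval is "whether or not the upper limit of the confidence interval exceeds the non-inferiority margin". The next sentence adds superiority tests for satisfaction, health and stigma.

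The closing paragraph on sample size supplies the only margin in either document: "The proposed sample size of 640 is sufficient based on a non-inferiority margin of 1.6 points in patient satisfaction (primary outcome"), with SD 8, power 0.8 and α 0.05 (sidedness not stated). The Aim 1 measures paragraphs name the Short Form-12 for caregiver health and a single-item measure for child health, without margin, SD or power. No instrument or scoring is given for stigma during hospitalization.

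**The concern.** To demonstrate that something does no harm, one has to exclude harm of a size that matters, normally by a confidence limit that falls short of a margin fixed in advance. The SAP does this for satisfaction. For the other three outcomes named in H2a it gives no margin. The wording that does apply to them treats the absence of a significant worsening as the result sought.

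On that wording, the trial could report that universal CRx-H does not diminish health or promote stigma while the intervals for those outcomes still include a small to moderate harm. This matters because the protocol (end of section A, full-trial version) says that the results will inform whether and how CRx-H is put into practice.

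**Working it through.** **1. The plan's own figure.** Inputs from the SAP, Aim 2 sample size paragraph: margin 1.6, SD 8, 1:1 allocation, power 0.8, α 0.05, total 640 (320 per arm). With a true difference of zero, n per arm = 2 × (z₁₋α + z₀.₈)² × (8/1.6)².

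- One-sided 5%: 2 × (1.645 + 0.842)² × 25 gives 310 per arm, 620 in total. Power at 320 per arm is Φ(0.2 × √160 − 1.645) = Φ(0.885) = 81%.
- One-sided 2.5%: 393 per arm, 786 in total. Power at 320 per arm is Φ(2.530 − 1.960) = 72%.

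So 640 is sufficient for satisfaction at one-sided 5% with complete data. In SD units the margin is 1.6/8 = 0.2.

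**2. What each H2a outcome has.**

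| Outcome | Margin | Stated harm criterion |
|---|---|---|
| Satisfaction | 1.6 points | Upper limit of usual care minus CRx-H against the margin |
| Caregiver health | none | No evidence of harm; not significantly diminished |
| Child health | none | No evidence of harm; not significantly diminished |
| Stigma | none | No evidence of harm |

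**3. How often a real harm would pass as non-significant.** The documents give no margin or SD for the three secondary outcomes, so this is an illustration. Assume a true harm of d SD, a two-sided 5% test, normal outcomes and an unadjusted comparison at one time point:

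P(non-significant) = Φ(1.960 − d × √(n/2)), with n per arm.

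| d | n per arm | Calculation | Result |
|---|---|---|---|
| 0.2 | 320 | Φ(1.960 − 2.530) | 28% |
| 0.2 | 256 | Φ(1.960 − 2.263) | 38% |
| 0.3 | 320 | Φ(1.960 − 3.795) | 3% |

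The value d = 0.2 is borrowed from the satisfaction margin. The 256 per arm is 640 × 0.80/2. The 80% is an assumption, taken from completion of the 1 and 3 month surveys in the earlier CRx trial (SAP, Aim 1, RCT Strategy).

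**4. What the interval leaves open.** At 320 per arm the 95% half-width is 1.960 × √(2/320) = 0.155 SD. An estimate of more than 0.2 − 0.155 = 0.045 SD in the harm direction therefore leaves 0.2 SD inside the interval, and up to 0.155 SD it is still non-significant.

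**5. Baseline adjustment.** Aim 2 takes over the Aim 1 mixed model, with interest in the "time (baseline and 7, 30, 90 and 180 days and 12 months post-discharge) by study arm interaction" and in contrasts at given time points. The SAP does not say whether the contrast is adjusted for baseline, with baseline means held equal, or is a change from baseline. With an assumed correlation of 0.5 between baseline and follow-up, d = 0.2 and 320 per arm:

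- ANCOVA-type model (variance factor 1 − r² = 0.75): Φ(1.960 − 2.530/√0.75) = 17%.
- Change from baseline (variance factor 2(1 − r) = 1): Φ(1.960 − 2.530) = 28%.

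Adjustment may therefore help or make no difference. Nor do the documents show a baseline measure of stigma during hospitalization; the baseline survey description lists stigma due to racial discrimination.

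**The case against.** The strongest reply is that the confidence-limit rule belongs to satisfaction alone. It comes straight after the satisfaction scoring, names one difference, one limit and one margin, and the sample size paragraph gives that margin for satisfaction. This is a fair reading. On it the rule is complete, and a reader who infers that the SAP tried to apply non-inferiority to four outcomes and failed goes further than the text. The label is attached to H2a as a whole, though, and the next sentence turns to all four outcomes, so the text is ambiguous. The gap does not depend on the answer: if the rule is for satisfaction only, the other three outcomes have no harm criterion beyond lack of evidence.

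A second reply is that superiority tests are planned for all four outcomes and that intervals are arguably implied. Both may be so. Failing to show superiority says nothing about absence of harm, and an interval does not settle the matter unless the plan says how it will be read.

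Third, these are secondary outcomes, and a formal margin for each would be demanding. That stands, and it is why the fix does not require margins.

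Fourth, the magnitudes rest on assumptions: 0.2 SD comes from another outcome, the retention from another trial. The planned imputation or weighting is ignored, and a normal approximation is rough for a single-item measure. That also stands; the figures show scale only.

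**Conclusion.** The point holds as a limit on what may be concluded. Aim 2 promises to demonstrate no caregiver or patient harm, but for caregiver health, child health and stigma the only stated criterion would let a non-significant result count as no harm. Under the assumptions above, a harm of 0.2 SD would pass 28% of the time at 320 per arm and 38% at 256; for 0.3 SD at 320 per arm it is 3%. The gap thus concerns small to moderate harms.

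Two further inferences are not supported. One is that the Aim 2 primary analysis is flawed on this account: satisfaction has a margin, a rule and a sample size. The other is that the rule looks at the wrong limit for stigma. That would follow only if the rule applies to stigma and higher scores mean more stigma, and the documents settle neither. It deserves a note, not a separate criticism.

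**What to change.** In the SAP, reword the Aim 2 purpose, Hypothesis 2a and the Aim 2 analysis text so that:

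- the non-inferiority label and the confidence-limit rule apply to satisfaction only;
- caregiver health, child health and stigma are reported as estimates with confidence intervals, with the direction of harm stated for each scale (for stigma, a note once its scoring is given);
- no conclusion of no harm is drawn from a non-significant result, and such a conclusion would need a justified, pre-specified margin that the harm-side confidence limit excludes.

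The satisfaction analysis stays as it is. The cost is wording only, with no new data. The downside is that the no-harm claim for these secondary outcomes is dropped or becomes harder to make. If a margin of 0.2 SD could be justified and there were no true difference, unadjusted power, Φ(0.2 × √(n/2) − z), at one-sided 5% and 2.5% would be 81% and 72% with 320 per arm, and 73% and 62% with 256 per arm.

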All caregivers randomized to CRxH will receive, in addition to the educational component and review of the HealtheRx, an initial text message (during the discharge process) and can reply “stop” at any time to prevent additional messages. Phone numbers will be verified via text message at the time of 7 day, 30 day, 90 day, 180 day and 12 month surveys and via text message each month in between follow-up surveys. The navigator will respond to text messages within 24 hours during regular work days and within 48 hours of weekends or holidays. The frequency and content of automated text messages sent to caregivers randomized to CRxH will be more frequent in the beginning of the intervention, decrease in frequency between 31-60 days of the intervention, and culminate in a final text at the end of the intervention at 90 days. The content of these messages is based on a text messaging experiment conducted during the the CMMI HCIA CRx study and provides proactive support from the resource navigator. The timing of these messages is informed by the Critical Time Intervention model.

Following randomization, the baseline survey will be administered in the hospital by a research interviewer blinded to the subject’s study arm. All caregivers will have received usual care at the time of the child’s admission and will also be blinded to the arm to which they are randomized. Discharge status of subject’s child will be monitored via the EMR. For caregivers randomized to the intervention, CRx-H will be delivered in the 48 hours pre-discharge. Follow-up surveys will be conducted by telephone using computer-assisted personal interviewing (CAPI) at 7, 30, 90 and 180 days and 12 months post-discharge. To maximize retention, we will use text messaging and phone calls, if needed, monthly between surveys to verify contact information, schedule and remind participants about upcoming surveys.

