Hypothesis 2b. Within the food secure caregiver group, those randomized to the CRx-H intervention will demonstrate a lower likelihood of becoming food insecure. In addition, they will exhibit a higher level of knowledge about food insecurity rates and support resources, more positive attitudes about welfare, and a higher likelihood of sharing resource information with others.

Strategy, Timeline, Methods, and Key Measures:

Aim 2 will utilize RCT data from both food secure and food insecure caregivers. For Aim 2, the primary outcome of interest is satisfaction with hospital care, specifically satisfaction with the discharge process. Satisfaction will be assessed 7 days post-discharge. After reviewing peer-reviewed literature as well as documentation of federal policy and payment models related to satisfaction with care, we narrowed the potential measures for assessing caregiver satisfaction to: (a) the Patient Satisfaction Questionnaire (PSQ) and (b) the Hospital Consumer Assessment of Healthcare Providers Survey (HCAHPS), and have chosen the latter. Developed and validated in 1976, the PSQ is designed for adult inpatients. HCAHPS, developed between 2002-05, was similarly designed to assess adults patients' and caregivers' experience of inpatient care. In 2015 with funding from AHRQ and

CMS, the Child HCAHPS was validated specifically to assess pediatric inpatient care. The global satisfaction and patient-provider communication sub-scales of the PSQ are the most relevant PSQ measures for our study. HCAHPS similarly assesses global satisfaction and patient-provider communication, but also specifically queries about satisfaction with the information provided at discharge, the segment of the hospital experience most likely to be affected by the CRx-H intervention. In addition, HCAHPS is being widely adopted into practice because performance on this measure informs value-based purchasing. We anticipate that the Child HCAHPS is on a similar trajectory. We selected the Child HCAHPS as our primary measure because it is targeted for pediatric hospitalizations, includes the dimension of satisfaction with discharge, and is likely to influence decision-making that could inform adoption and sustainability of the CRx-H intervention. To our knowledge, the CRx-H trial will be the first randomized trial to assess the impact of a self- and family management intervention on satisfaction with hospital care among food secure and food insecure caregivers.

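### Aim 2 non-inferiority: keep intent-to-treat, but report the share of CRx-H sessions held before discharge and one supportive estimate scaled by it

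*SAP*

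**What the plan says.** SAP Aim 2 sets out to show that "a universal approach to delivery of the CRx-H intervention does not diminish caregiver satisfaction with care". The primary outcome is the Child HCAHPS discharge composite (0 to 100), asked 7 days after discharge about the index stay. The SAP chose it because discharge information is "the segment of the hospital experience most likely to be affected by the CRx-H intervention".

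On analysis, SAP Aim 2 states "We will use the analytic approach described for Aim 1, following the principles of intent-to-treat", and the Aim 1 text that it takes over reads "The main analyses will follow the principle of intent-to-treat". Hypothesis 2a is judged on the confidence interval for usual care minus CRx-H, and on "whether or not the upper limit of the confidence interval exceeds the non-inferiority margin".

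On delivery, the SAP (Aim 1, RCT Strategy) states "For caregivers randomized to the intervention, CRx-H will be delivered in the 48 hours pre-discharge". The full-trial protocol (B1, B2) has an interventionist schedule a remote session after randomization, earlier in the stay. The discharging nurse then hands over a printed HealtheRx, and electronic copies and text messages are also sent. Fidelity tracking is named only for the nurse's booster (B2).

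The other analyses named for Aim 2, or carried over from Aim 1, are superiority tests, optional case-mix adjustment, interactions, food-secure-only analyses, missing-data methods, and moderation and mediation. None uses receipt of the session or its timing. Protocol section C allows further a priori analyses as needed but names none.

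**The concern.** In a superiority trial, non-receipt works against the sponsor. In a non-inferiority trial it can work in the sponsor's favour: if the intervention does harm, caregivers who were assigned to it but missed it shrink the observed harm. A session held after discharge, or never held, cannot have shaped the discharge that the caregiver rates at 7 days.

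Some missed sessions are plausible. Recruitment runs to 72 hours after admission (Protocol B7), and only admissions under 24 hours are excluded (B9). Consent, baseline survey, randomization, an alert, assignment of an interventionist and contact must all come before the session (B1).

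What is at stake is how the result will be read. The SAP presents Aim 2 as an answer to physicians' worry that intervening lowers satisfaction. Many readers will take a positive result to mean that families who received CRx-H were no less satisfied. If delivery is incomplete, the planned analysis does not show that by itself.

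**Working it through.** **Inputs from the SAP (Aim 2, Analysis and Sample Size Justification).** N = 640 at 1:1, so 320 per arm; SD 8; margin 1.6; alpha 0.05, sidedness not stated; power 0.8. All 320 per arm are taken to contribute an outcome.

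**Inputs assumed, because the documents give none.** The share p of the CRx-H arm with the session before discharge is 0.9 or 0.8. The fraction k of the effect kept by a caregiver who misses the session but has boosters and texts is 0 (an upper bound on dilution) or 0.5.

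**1. Reproduce the plan's figure.** SE = 8 × √(2/320) = 0.632. Power at true equality = Φ(1.6/0.632 − 1.645) = 0.812, and 80% power needs 310 per arm (620 in total). So 640 is sufficient at one-sided 0.05, which is used below. At one-sided 0.025, power is 0.716.

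**2. Dilution.** Let d be the true loss in recipients and e = p + k(1 − p). The intent-to-treat difference is d × e, and

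P(non-inferiority declared) = Φ((1.6 − d × e)/0.632 − z).

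With d = 1.6:

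| Missed | k | e | ITT difference | z = 1.645 | z = 1.960 |
|---|---|---|---|---|---|
| 0% | – | 1.00 | 1.60 | 5.0% | 2.5% |
| 10% | 0.5 | 0.95 | 1.52 | 6.4% | 3.3% |
| 10% | 0 | 0.90 | 1.44 | 8.2% | 4.4% |
| 20% | 0.5 | 0.90 | 1.44 | 8.2% | 4.4% |
| 20% | 0 | 0.80 | 1.28 | 12.7% | 7.3% |

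**3. Other true states (z = 1.645).** With d = 0 the chance of success is 81.2% at any p. With a 1-point gain in recipients and k = 0, it goes from 99.3% (none missed) to 98.4% (20% missed). The effect described here arises only if CRx-H does harm.

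**4. The supportive estimate.** Divide the intent-to-treat difference and its limits by p. The point estimate then targets d × e/p. For k between 0 and 1, p ≤ e ≤ 1, so for a loss

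d × e ≤ d ≤ d × e/p.

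The intent-to-treat and scaled estimates therefore bracket the recipient effect in expectation. With k = 0.5 and d = 1.6:

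- 10% missed: 1.52 and 1.6 × 0.95/0.9 = 1.69.
- 20% missed: 1.44 and 1.6 × 0.90/0.8 = 1.80.

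**5. Its price.** The chance that the scaled upper limit falls below 1.6 at true equality is Φ(1.6p/0.632 − 1.645): 73.6% at p = 0.9 and 64.8% at p = 0.8, against 81.2% for intent-to-treat.

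**The case against.** The strongest reply is that the plan's question is already answered. Hypothesis 2a compares caregivers as randomized and the aim concerns universal delivery, so intent-to-treat is the matching analysis, and the SAP promises no separate statement about recipients. This stands. It is why the primary analysis should not change.

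A reader might infer from the table that the planned test has a false-positive rate of 8% to 13%. The documents do not support that. With 10% or 20% missed and nothing kept, the true randomized difference is 1.44 or 1.28, inside the margin, and declaring non-inferiority is correct for H2a. The rates are errors only against a hypothesis about recipients.

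A reader might also infer that many sessions will be missed. No missed share is given, and there are safeguards: recruitment takes account of the anticipated discharge date (Protocol D7), the session is meant to come earlier in the stay (B2), and under the SAP the discharge status of the subject's "child will be monitored via the EMR". The dilution is small if nearly all sessions precede discharge.

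Finally, k = 0 is an extreme case. The SAP ties the outcome to CRx-H as a whole, and the printed HealtheRx given at discharge is the component closest to it. No text makes that handover, or the texts, conditional on a completed session. The same fact weakens the complier-average estimate, which assumes that assignment without a session has no effect. This also stands, so the estimate should be read as one end of a range.

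**Conclusion.** This is a cheap improvement and not an error in the plan. Intent-to-treat is valid for H2a and should remain its only basis. The gap is that neither document plans to use whether the session preceded the rated discharge, so a positive result would support offering CRx-H universally without, on its own, showing that receiving it is harmless.

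The size is unknown because it depends on an undocumented missed share. Over the assumed range of 10% to 20% missed, a recipient loss equal to the margin would pass between 6.4% and 12.7% of the time, against 5.0% with full delivery. The lower part of that range is more plausible, given the boosters and texts. All of this assumes one-sided 0.05, SD 8, complete outcome data and a true harm in recipients; nothing in the documents suggests that such harm exists.

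**What to change.** Add one paragraph to SAP Aim 2:

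- Record the date of the core session against the discharge date. Count a session held after discharge, or not held, as not delivered before discharge.
- Report the share of the CRx-H arm with the session before discharge.
- Pre-specify one supportive complier-average estimate for the discharge composite: the intent-to-treat difference and its limits divided by that share, shown beside intent-to-treat. State that the pair brackets the recipient effect if a missed session keeps between none and all of it.
- State that this estimate qualifies any statement about recipients and is not a second gate for H2a.

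The cost is one date field and one supportive result. Discharge date is already held (Protocol D6). Session time must be known in practice, because the HealtheRx is sent within 24 hours of the session (B2). Sample size, alpha and the primary test do not change.

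The downside is a wider limit, which may miss 1.6 even when the arms are truly equal. The scaled estimate also overstates a loss if boosters and texts carry part of the effect, for example 1.69 or 1.80 for a true 1.6 when half is kept at 10% or 20% missed. If delivery proves near-complete, the reported share alone shows that dilution was negligible.
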